## **2.2. Objectives**

The aims of the research are:

1. To establish the impact of HIVST distribution through peer networks with improved access and enhanced community support structures on the uptake of PrEP in men.
2. To conduct a process evaluation of the intervention in this typical rural African population and characterize peer networks.
3. To quantify the population level impacts and cost-effectiveness of male peer to peer HIVST distribution strategies on the uptake of PrEP in HIV hyper-endemic settings

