- iv. After seven days the helpdesk will contact the distributor and the intended recipients to ascertain whether kits have been received and used, to collect behavioural HIV risk data for the recipients and encourage attendance at a healthcare facility for a confirmatory test. HIVST recipients will be invited to complete the informed consent over the telephone and be enrolled in the study. Follow-up calls will be made to these individuals if necessary. Recipients will be encouraged to consider becoming distributors and advised on the location of community facilities (shops, pharmacies, hairdressers etc.) from where they can obtain the HIVST packs for distribution. This method of HIVST distribution through community-based hubs has been proven to be successful in studies in other Sub-Saharan African settings. [48] A small renumeration of \$1 per peer will be transferred electronically to the initial distributor for each kit successfully distributed. Successful distribution to peers is defined as the peer having received the HIVST and has been successfully contacted by the helpline to confirm receipt of the HIVST but does not have to use the HIVST or agree to enrol in the study as a distributor. Names and cell numbers will be collected for intended recipients by the study team and held confidentially.

- v. If the recipient chooses to become a distributor they will go to the facility and the owner will check using a real-time database that they have not already received a pack of kits for distribution. If they pass this screening, they will be given a pack of three HIVST kits for within cluster distribution, again A small renumeration will be paid to the facility owner for each pack of kits given out.
- vi. After seven days the helpdesk will contact the second level recipients and steps iv) and v) will be repeated until all kits allocated to a particular community have been distributed.
- vii. When participants attend a clinic for confirmatory testing, they will return the HIV test kit packaging with the unique label and based on their self-reported HIVST result (unreactive/reactive) be screened for PrEP or ART. The outcome of the screening will be recorded in a tick-box on the label and the packaging deposited in a secure box at the clinic from where it will be collected by the study team.

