### **3.3.3 HIV risk self-assessment tool**

Previous work has indicated that males in this community have a low level of perception of their risk of HIV infection. [41, 50] To address this, a tool will be developed that will allow study participants to make a self-assessment of their level of risk. Information on how to use the tool will be provided to all recipients of HIVST kits including the primary distributors as part of the kit insert. They can use this tool multiple times during the study period as their risk profile may change over this time. All SMS messages will be free, and no identifying data will be collected by the study team. After submission of an SMS users will be prompted by an automated interactive system to provide a numerical response to a series of behavioural risk questions. The questions will be the same as those used in the national PrEP screening tool. Based on the responses they will receive an automated message indicating whether they have a high level of risk and if so recommending that they consider PrEP initiation.

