## **3.4 Outcomes**

**The primary outcome** of the trial will be the proportion of men initiating PrEP out of all men aged 18 and over.

**Secondary outcomes will include:** i) the proportion of men self-testing for HIV over the period of the intervention out of all men aged 18 and over. and ii) the proportion of screened men adhering to PrEP or ART six months after initiation, measured by laboratory analysis of dry blood spots, out of all men initiating PrEP or ART after receiving an HIVST kit.

The qualitative performance evaluation will inform work to combine several quantitative data sources to evaluate how the intervention spread through social networks, and how network position and structure affected trial outcomes. We will combine information on intended and actual HIVST recipients with the existing Manicaland census data to measure what proportion of PrEP/ART eligible men were reached by our intervention. We will assess the level of network saturation achieved by the distribution process [16], and whether our approach reached individuals at higher risk of HIV acquisition as the recruitment process advanced – a key aim of the respondent driven sampling (RDS) methods on which our peer recruitment methods are based. Using entity resolution algorithms and hand-checking, we will identify linkages across distribution chains, and from this build network graphs of connections between men in the study areas. We will use these graphs to describe the structure of local male peer networks and statistically evaluate how characteristics of distributors and their social contacts influenced network distribution process and subsequent engagement with care. We will also evaluate whether intervention success differed across study clusters based on cluster-level network structures (e.g., density, clustering, age, and risk homophily) as well as by non-network characteristics (e.g., urbanicity, economy). Finally, once wider geographic distribution occurs in the second trial phase, we will evaluate whether distribution chains overlap and if greater geographical distribution affects study outcomes. We expect that our work will explain variation in outcomes and detail the contextual factors to consider when replicating or taking this intervention to scale. [33] We also expect to develop light-touch tools for use by implementors pre- and during implementation of such interventions, which can guide localization of this socially mediated design.

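### Secondary outcome (ii) pools adherence to PrEP and to ART in one proportion compared between arms, so a change in the PrEP/ART mix can look like an effect on adherence.

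*Protocol*

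**What the plan says.** Section 3.4 of the protocol gives secondary outcome (ii) as "the proportion of screened men adhering to PrEP or ART six months after initiation", measured from dried blood spots, "out of all men initiating PrEP or ART after receiving an HIVST kit". Both drugs share one numerator and one denominator. No section defines a PrEP-only or an ART-only adherence outcome. The primary outcome, by contrast, concerns PrEP alone: "the proportion of men initiating PrEP out of all men aged 18 and over".

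Section 3.3.1, step vii, describes how men reach each drug. At the clinic they will, "based on their self-reported HIVST result (unreactive/reactive) be screened for PrEP or ART", and staff tick the outcome of that screening on the kit label.

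Section 5.3 applies the intention-to-treat test of the intervention effect to primary and secondary outcomes alike, using a Poisson model with log link and cluster random effects. It states no separation by drug. Section 3.6 sizes the trial on PrEP initiation of 2% in control against 8.8% in the intervention arm.

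**The concern.** Routing by self-test result means the PrEP and ART groups are different men. A pooled adherence proportion is a weighted average of two drug-specific proportions, and the weight is the PrEP share of initiators. The intervention is built to change the number of PrEP initiators, so it is likely to change that weight.

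The denominator of outcome (ii) is therefore itself affected by the intervention. An arm contrast on the pooled figure mixes two things: whether men on each drug adhere better or worse, and whether the arms have different proportions of men on each drug. If PrEP adherence is the lower of the two, success on the primary outcome pulls the pooled figure down in the intervention arm and can be read as harm to adherence. If it is the higher, the bias runs the other way. The level of the figure within an arm has the same problem: one pooled value is compatible with a range of PrEP adherence values.

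**Working it through.** **1. The plan's own count (section 3.6).**
PrEP initiators per intervention cluster: 90 × 0.70 × 0.80 × 0.33 × 0.43 = 7.15. Over 22 clusters: 157. Against half of 3,591 men (1,795.5): 157.3 / 1,795.5 = 8.8%. This reproduces the stated figures. In control, 2% × 1,795.5 = 35.9, about 36 men.

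**2. A range for ART initiators (assumed; the protocol gives none).**
Self-testers in the intervention arm: 90 × 0.70 × 0.80 × 22 = 1,109. If 2% to 10% are reactive and 50% to 100% of those start ART, there are 1,109 × 0.02 × 0.50 = 11 to 1,109 × 0.10 × 1.00 = 111 ART initiators. The PrEP share runs from 157/168 = 0.93 to 157/268 = 0.59. The illustration below uses 50 per arm.

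**3. The pooled figure by arm.**
Formula: pooled = (n_PrEP × p_PrEP + n_ART × p_ART) / (n_PrEP + n_ART). Assume p_PrEP = 50% and p_ART = 80% in both arms, and that all initiators belong in the denominator.
- Intervention: (157 × 0.50 + 50 × 0.80) / 207 = 118.5 / 207 = 57%.
- Control: (36 × 0.50 + 50 × 0.80) / 86 = 58 / 86 = 67%.

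The difference is −10 points, or a ratio of 0.572 / 0.674 = 0.85 on the scale of the log-link model, although adherence to each drug is identical in the two arms.

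**4. How far this depends on the assumptions** (157 and 36 PrEP initiators throughout).

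| ART starts, intervention / control | PrEP, ART adherence | Intervention | Control | Difference (points) |
|---|---|---|---|---|
| 11 / 11 | 50%, 80% | 87.3/168 = 52.0% | 26.8/47 = 57.0% | −5 |
| 50 / 50 | 50%, 80% | 57.2% | 67.4% | −10 |
| 111 / 111 | 50%, 80% | 167.3/268 = 62.4% | 106.8/147 = 72.7% | −10 |
| 50 / 50 | 70%, 80% | 149.9/207 = 72.4% | 65.2/86 = 75.8% | −3 |
| 48 / 11 (ART rises by 157/36, as PrEP does) | 50%, 80% | 116.9/205 = 57.0% | 57.0% | 0 |

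**5. Level within one arm.**
With a PrEP share of 0.7, a pooled 60% fits PrEP adherence of (0.60 − 0.3 × 1.00)/0.7 = 43% if ART adherence is 100%, and 60% if ART adherence is 60%.

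**6. Precision after a split.**
PrEP, intervention arm, at an assumed 40%: design effect 1 + (7.15 − 1) × 0.1 = 1.6; 95% half-width 1.96 × √(0.4 × 0.6 × 1.615 / 157) = 9.7 points. PrEP, control arm, 36 men: 1.96 × √(0.24/36) = 16 points before clustering. ART at 80%: 1.96 × √(0.16/50) = 11 points with 50 men and 1.96 × √(0.16/11) = 24 points with 11, before clustering.

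**The case against.** The best case for pooling is that the protocol treats care after a self-test as one pathway. Monthly support calls cover both drugs (3.3.1 step ix, 3.3.7), and so does the telephone support in 3.7. A pooled figure for sustained engagement, whatever the test result, fits that view, and reporting by drug alongside it is often left to an analysis plan, which is not shown here. This stands as a reason to keep a pooled figure as description. It does not rescue the pooled figure as a between-arm test: the protocol fixes that definition itself, and the drug mix moves the result.

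It is also fair that the size rests entirely on assumed rates and counts, and that the intervention may raise ART starts too. Where ART starts rise in the same ratio as PrEP starts, the arm contrast is not distorted. Nothing in the protocol leads one to expect that exact proportionality.

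A reader might be tempted to go further in four ways that the protocol does not support.
- *All the objectives concern PrEP.* In section 2.2, aim 2 is a process evaluation and does not name PrEP; aims 1 and 3 concern effects "on the uptake of PrEP in men", which is uptake, and the PrEP-only primary outcome measures that.
- *The three- and ten-year projections take outcome (ii) as input.* Section 3.3.9 names self-testing uptake by age as the secondary-outcome data used, and assumes that PrEP uptake is maintained.
- *Splitting the outcome deals with men who stop PrEP because their risk fell.* Section 3.3.3 says men can reuse the risk tool "as their risk profile may change over this time" but says nothing about stopping PrEP, and a PrEP-only proportion would count such a man in the same way.
- *PrEP persistence cannot be learned from this trial.* That is true of the pooled outcome, not of the records beneath it.

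**Conclusion.** The point holds as a defect in the definition of one secondary outcome. As written, the arm contrast on outcome (ii) can show a difference when adherence to each drug is the same in both arms. Under the illustrative assumptions the artefact is about 10 points (57% against 67%), and across the variants tried it runs from 0 to about 10. It needs two conditions: adherence differs by drug, and the PrEP share of initiators differs by arm. The sample-size target makes the second likely. The protocol gives no figures on the first. The effect is small if the rates are close or nearly all initiators in both arms are on PrEP.

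The control count of 36 assumes that every control PrEP initiator had received a self-test kit and so belongs in the denominator. The primary outcome, its sample size and its stated power are unaffected. The change is worth making before data are analysed, because it is cheap and the pooled result could be misread in either direction.

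**What to change.** Replace outcome (ii) with two outcomes in section 3.4:
- (iia) adherence at six months confirmed by dried blood spot, out of men initiating PrEP;
- (iib) the same, out of men initiating ART.

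Classify men by the screening outcome recorded on the kit label. Section 3.3.1 describes the monthly calls and the single tenofovir diphosphate assay jointly for both drugs, so neither should be relied on to tell the drugs apart. The tick-box options are not itemised, so the sponsor should confirm that they separate PrEP from ART. State in section 5.3 that each outcome is analysed separately by arm and that any pooled figure is descriptive only.

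The cost is wording plus that check of the label, with no new visits, specimens or participants. The price is precision: about ±10 points for (iia) in the intervention arm, wider in control, and (iib) may be imprecise if few men start ART.

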### 3.5 Participant timeline

The follow-up schedule for recipients of HIVST kits is shown in figure 4.

[figure not shown]

Figure 4 Timeline for engagement with participants after HIVST kit distribution

### 3.6 Sample size

Based on data on HIV risk collected in the 2020/21 surveillance round we estimate that 33% of men aged 18 and over, will fulfil the requirement for PrEP initiation. A comparable study indicated that 43% of those identified as at risk would take-up PrEP. [18] In the 2020/21 surveillance round 3/3591 (0.14%) men were currently using PrEP. With a continued roll-out of PrEP until the start of the study, we assume a baseline PrEP usage of 1% which will increase to 2% over the course of the trial in control communities. The study will use a cluster-randomised trial design. To have sufficient men in each cluster to explore multiple waves of network recruitment we will create 22 clusters in the intervention arm and 22 in the control, from a total population of 3591 men which equates to 81 men in each cluster. The clusters will be created from either a single village or groups of neighbouring villages. In each intervention cluster a maximum of 90 HIVST kits will be distributed, assuming that 70% of these kits reach men in the cluster, 80% of these men use the HIVST, 33% of these are eligible for PrEP and 43% of these initiate PrEP, we estimate we will have 7.15 men / cluster initiating PrEP a total of 157 men. This represents 8.8% of the study population in the intervention clusters. Using an Intra-Cluster correlation coefficient of 0.1, a conservative estimate based on data collected in similar settings [58] and with a total sample size in the intervention and control arms of 3591 we will have greater than 85 % power to detect a difference in the percentage of men initiating PrEP from 2% in the control arm versus 8.8% in the intervention arm.

### 3.7 Recruitment

The initial distributors will be identified by the research team as described above. We will have an initial target number of distributors e.g., 5 per intervention cluster. We will have target recruitment of 63 men in each cluster. If it becomes clear that the target recruitment for an individual cluster will not be reached, we will identify further initial distributors in the cluster and re-start the distribution process. We will provide telephone support for study participants to maximise adherence to PREP/ART and maintain retention in the study.

### 3.8 Study timeline

Years	1				2				3				4				5			
	q1	q2	q3	q4																
Start-up activities (protocol, training, sms-app development, community entry )																				
Iterative prototyping																				
Within-cluster distribution - Kits distributed for 6 months in each cluster over 18 months																				
Wider distribution 2 months in each cluster over 6 months																				
Follow-up of study participants up to a maximum of 6 months after screening																				
Process evaluation (pre-intervention) – Refinement of logic model																				
Process evaluation (during-intervention) – Continuous feedback																				
Post-intervention evaluation ( who, what , when , where , how)																				
Analysis write-up and dissemination of results																				

Figure 5 Planned timeline for the study

## 4 Methods: Assignment of interventions

### 4.1 Allocation

All participants will be assigned to clusters consisting of one or more distinct villages as described in the sample size section of this protocol. Clusters will be randomly assigned to either the intervention or the control arms of the study. Allocation will be stratified on the basis of the five major socioeconomic strata in Manicaland; small towns, agricultural estates, roadside settlements, subsistence farming areas and urban areas environments.

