## **5.3 Statistical methods for analysing primary and secondary outcomes**

For the test of the intervention effect on the primary and secondary outcomes will be conducted using the intent-to-treat (ITT) analysis for all men randomized at the community level. We will define our intent to treat population as those clusters who were randomized to intervention and control groups. We will use generalized linear models with Poisson distribution, log link function and robust error terms, adjusting for community-level clustering through random effects.

Analysis of baseline data will be carried out once recruitment has completed in all clusters. Final analyses will begin following field data and all associated data cleaning and quality control procedures. No interim analyses will be conducted.

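### Clusters are randomised within five socioeconomic strata (4.1), but the model stated in 5.3 has no stratum term; if strata predict PrEP initiation, an otherwise valid standard error would be somewhat too large (minor)

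*Protocol*

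**What the plan says.** Section 4.1 of the protocol randomises clusters, not men, and states: "Allocation will be stratified on the basis of the five major socioeconomic strata in Manicaland". The five strata are small towns, agricultural estates, roadside settlements, subsistence farming areas and urban areas.

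Section 5.3 gives the model for the primary and secondary outcomes: "We will use generalized linear models with Poisson distribution, log link function and robust error terms", followed by "adjusting for community-level clustering through random effects". It names the distribution, link, type of standard error and one adjustment. It does not mention the strata, and nothing elsewhere in the protocol brings them into the effect analysis. Section 3.4 plans to explore whether success differs by urbanicity and economy, but that concerns heterogeneity and is not adjustment of the primary model.

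Section 3.6 gives the design figures: "we will create 22 clusters in the intervention arm and 22 in the control", 3591 men in all (about 81 per cluster), an intra-cluster correlation of 0.1, and more than 85% power for a difference "from 2% in the control arm versus 8.8% in the intervention arm".

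**The concern.** Stratified allocation balances the strata across arms by design, so differences between strata add little to the true sampling spread of the effect estimate. A model without stratum terms does not take this into account. It leaves the between-stratum variation in the between-cluster residual and counts it in the standard error. Neither a community random effect nor a robust variance removes it.

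What is at stake is how honestly the reported uncertainty is stated, and a small amount of precision. There is no bias. Section 4.2 says that analysts cannot be blinded, so the use of strata is better fixed before outcome data are seen.

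**Working it through.** **Inputs from the protocol.** 22 clusters per arm, 3591 men, 3591/44 = 81.6 men per cluster (3.6 gives 81), ICC 0.1, 2% versus 8.8%.

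**Assumptions.** Two-sided alpha of 0.05 (not stated). Stratum share *s* of between-cluster variance of 0%, 10% or 25% (the protocol gives no figure). Number of clusters per stratum (not given; the main simulation uses 10/8/8/8/10).

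**1. The plan's own power.** Design effect = 1 + (81 − 1) × 0.1 = 9.0. Effective number per arm = 22 × 81 / 9.0 = 198. Power for 2% versus 8.8% is 85.2% by the two-proportion formula and 85.7% with unpooled variance. The stated figure reproduces, and the formula takes no credit for stratification.

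**2. Closed form for the omitted strata, with otherwise valid standard errors.** The between-cluster part of the variance of a cluster proportion is B = ICC × m / (1 + (m − 1) × ICC) = 0.1 × 81.6 / 9.06 = 0.90.

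Ratio of reported to true standard error = √[(1 − sB + sB × 22/21) / (1 − sB)].

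- s = 0: 1.000
- s = 0.10 (sB = 0.090): √(1.0043/0.910) = 1.051
- s = 0.25 (sB = 0.225): √(1.0107/0.775) = 1.142

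Without the 22/21 term and with m = 81, the excess is 4.8% and 13.6%. A normal test with errors of that size would have type I error of 4.0% and 2.6%.

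**3. Simulation of the model in 5.3.** Poisson log-link model with a normal random intercept and cluster sandwich errors; 44 clusters of 82 men; lognormal cluster risks matched to ICC 0.1; share set on the log scale; 1:1 allocation within strata; 8,000 trials with no effect per setting (Monte Carlo error about 0.25 points). The simple correction multiplies the variance by G/(G − p), with G clusters and p model coefficients, and uses t on G − p degrees of freedom.

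| Shares 0 / 10 / 25% | 2% in both arms | 5% in both arms (assumed rate) |
|---|---|---|
| True SD of log ratio, no strata | 0.549 / 0.525 / 0.504 | 0.376 / 0.360 / 0.338 |
| True SD of log ratio, with strata | 0.551 / 0.526 / 0.503 | 0.377 / 0.360 / 0.339 |
| Corrected SE ÷ true SD, no strata | 0.98 / 1.02 / 1.06 | 0.99 / 1.04 / 1.10 |
| Type I error, no strata, uncorrected z | 6.9 / 5.4 / 4.7% | 6.6 / 5.4 / 4.1% |
| Type I error, no strata, corrected | 5.6 / 4.4 / 3.7% | 5.4 / 4.4 / 3.0% |
| Type I error, with strata, corrected | 6.2 / 5.6 / 5.9% | 5.8 / 5.4 / 5.4% |

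Adjustment does not change the true spread; only the reported error differs. At 2% the excess at shares of 10% and 25% is 2% and 6% against the true SD, or 4% and 8% relative to the zero-share ratio (1.02/0.98 and 1.06/0.98). Both are below the closed form. Also at 2%, adding strata with uncorrected z tests gives type I error of 9.2 / 8.4 / 8.7%. A leverage-based correction with strata gives 5.8 / 5.3 / 5.5%.

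**4. What uncorrected robust errors do.** The ratios above are for corrected errors. Dividing by √(44/42) = 1.0235 gives uncorrected ratios of about 0.96 / 1.00 / 1.04 at 2% and 0.97 / 1.02 / 1.07 at 5%.

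At 2% versus 8.8% (3,000 trials), corrected intervals without strata are 1.001 / 1.032 / 1.094 times as wide as corrected intervals with strata. Dividing by 1.0235 and by 2.018/1.960 = 1.030 gives 0.95 / 0.98 / 1.04. Uncorrected intervals without strata are thus about 5% narrower, 2% narrower and 4% wider than stratified, corrected ones.

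**5. Dependence on the estimator.** A marginal Poisson model with cluster-robust errors shows the same pattern at different levels. Without strata, its SE-to-SD ratio is 0.83 / 0.85 / 0.88 at 2%. With strata and the simple correction, its type I error is still about 7% to 9%.

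**6. Stratified cluster-level t test.** At 2%, type I error is 3.5 / 3.3 / 3.5%, against 3.5 / 2.9 / 2.5% unstratified. Power at 2% versus 8.8% is 92.7 / 93.8 / 94.7%, against 92.8 / 93.4 / 93.7%.

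**The case against.** The strongest reply is that this is analysis-plan detail. Section 5.3 describes the model in one sentence, does not say that community is the only adjustment, does not exclude covariates and does not name a z test. Sections 4.1 and 5.3 do not contradict each other. For small-sample corrections and the choice of z or t this stands: their absence is no fault of the protocol. It stands less well for the strata. Section 5.3 commits to a model, down to its one adjustment, and leaves out the factor on which clusters are randomised.

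The second reply is that harm is not shown for the model as written. This stands in part. A reader might infer that the test is conservative and its intervals too wide. The protocol does not support that, because uncorrected robust errors with 44 clusters run small. In the random-intercept simulation type I error is then 4.1% to 5.4% at shares of 10% and 25%, and the interval may be narrower or wider than the stratified one.

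Third, the size rests on assumed shares and stratum sizes, and it is zero if strata are not prognostic. That is correct.

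Fourth, the remedy is not free of problems. Adding strata alone makes type I error worse, and sparse strata can break the model. That is also correct, and it shapes the fix.

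**Conclusion.** The point holds as a minor one. The stated model omits the randomisation strata. With otherwise valid standard errors, the reported standard error would be about 5% to 14% too large by closed form at assumed stratum shares of 10% to 25%, less at a 2% event rate, and unaffected at a share of zero.

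Three stronger readings are not supported:

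- **The stated power is wrong.** It reproduces at 85.2% and does not depend on the strata.
- **The estimate is biased or more variable.** Its true spread is the same with and without stratum terms.
- **The analysis is conservative as it stands.** That depends on how the robust errors are computed, and exact type I levels depend on the estimator.

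The omission and the textual facts are certain. The size is not, since it rests on stratum shares and cluster counts per stratum that the protocol does not give.

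**What to change.** In 5.3, state that the primary and secondary analyses follow the randomisation strata, in one of two ways:

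- Add the five-level stratum as a fixed effect, together with a small-sample correction to the robust errors (leverage-based is safer at low event rates) and t-based inference.
- Use a stratified cluster-level analysis with t-based inference. This should also be the named fallback if a stratum has no events.

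Do not add strata with uncorrected robust z tests.

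The cost is one or two sentences and four degrees of freedom (42 to 38; critical t 2.018 to 2.024). If strata are not prognostic, simulated cluster-level power moves from 92.8% to 92.7%. The cluster-level test is mildly conservative at a 2% event rate (3.3% to 3.5%).

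The fallback is needed. At 2% in both arms, some stratum has no events in 1.0%, 1.9% and 4.3% of simulated trials at shares of 0%, 10% and 25%. If the lowest-risk stratum has only 6 clusters, this rises to 8% and 14% at shares of 10% and 25%.
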